9.1.2 Method of Analysis

Descriptive statistics (number of subjects observed, mean, standard deviation, median, minimum, and maximum) will be presented by treatment group for each visit and the change from the baseline in the total score of the PSP-rating scale after 24 weeks (6 months) of investigational product administration. To test the difference between each study group and the control group (GV1001 0.56 mg/day vs. control group, GV1001 1.12 mg/day vs. control group), an MMRM analysis will be conducted with the treatment groups, visits, and interactions between the visits and the treatment groups set as fixed effects, and the subjects set as the random effect, as well as considering the baseline values, age, and sex as covariates. The results of the MMRM analysis will be summarized by LSM and standard error (SE) for each treatment group, the LSM difference between the study groups and the control group (GV1001 0.56 mg/day vs. control group, GV1001 1.12 mg/day vs. control group) and its 95% confidence interval as well as the two-side p-value.

Additionally, testing the difference within each treatment group will be conducted by the same MMRM analysis.

MMRM constructed as follows

- Dependent Variable: Change from baseline in total score of PSP-rating
- Fixed Effects
 - Fixed Continuous Effects: Baseline PSP-rating, Age
 - Fixed Categorical Effects: Treatment, Visit, Visit*Treatment, Sex
- Repeated Effect: Visit
- Random Effect: Subject
- Covariance Structure: Unstructured (UN)

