11. SUBGROUP ANALYSES

Subgroup analyses for efficacy will be conducted on the endpoint related with PSP-rating scale, modified PSP-rating scale 10 and modified PSP-rating scale 14 for FAS using the same analysis methods (refer to 9.1 and 9.2).

Subgroup Variable	Category
PSP Type	
• Richardson type [PSP-RS]• Parkinsonian type [PSP-p]

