5.3. Inclusion Criteria

- 1) Patients aged \geq 41 years to \leq 85 years
- 2) Patients clinically diagnosed with a probable PSP (Richardson type [PSP-RS] or parkinsonian type [PSP-p]) by the diagnostic criteria for PSP developed by the International Parkinson and Movement Disorders Society Task Force
- 3) In the case of the PSP-RS type, patients with clearly identified supranuclear ophthalmoplegia (SOP) according to the judgment of the investigator (e.g., the sum of scores in the ocular motor part of the PSP-rating scale must be \geq 5 points or the downgaze [voluntary downward command movement] score must be \geq 2 points). In the case of the PSP-p type, patients identified as having shown little or no response to previous administration of levodopa according to the judgment of the investigator during the course of treatment
- 4) Patients who had been taking a stable dose of a neurological drug for at least 1 month prior to screening without changes in the dose
- 5) Patients who are able to walk 3 meters or more independently or with assistive devices
- 6) Patients with at least 15 points on the Korean Mini-Mental State Examination (K-MMSE) at the screening visit (however, the results of a test performed at the study site within 2 weeks prior to the screening visit may be used if available)
- 7) Patients who have a guardian who can accompany the patient at all visits according to the schedule of this clinical study, and who is able to supervise the subject's compliance with the test and examination procedures performed at the visits and provide information on the subject's indication, and whose guardians have provided a written consent for participation in the clinical study
- 8) Patients and/or their representatives who have voluntarily provided a written consent for participation in this clinical study

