6.3. Randomization

Subjects who provide a written consent to participate in this clinical study will be assigned a screening number consisting of [study site number: 2 digits]-S-[serial number: 3 digits] in the order in which the written consent was obtained. Subjects who meet the inclusion and exclusion criteria will then be randomized according to the randomization plan, and will be assigned a unique randomization number consisting of [study site number: 2 digits]-R-[serial number: 2 digits] in the order in which the investigator decided to enroll the subjects. Subjects who meet the inclusion and exclusion criteria will be assigned sequentially according to the order of randomization at each study site.

A randomization table will be generated by an independent statistician not related to this clinical study prior to the start of the clinical study by using SAS® (Version 9.4 or higher; SAS institute, Cary, NC, USA), and the table will be generated to allow assignment of subjects to Study Group 1, Study Group 2, or the control group at a 1:1:1 ratio by applying a stratified block randomization method. Subjects who are enrolled in this clinical study and ultimately determined to be eligible to participate in the clinical study will be assigned a randomization number sequentially through the Interactive Web Response System (IWRS), and afterward, the subjects will be assigned to Study Group 1, Study Group 2, or the control group and receive a unique IP number.

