11.2.3. Covariate Adjustment

Efficacy endpoints will be analyzed with adjustments for the baseline values as well as for the age and sex.

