11.2.6. Subgroup Analysis

Subgroup analysis will not be considered in this clinical study.

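### The primary MMRM does not adjust for PSP type, the only factor the SAP splits efficacy by, so a chance imbalance in type would go unadjusted if type is prognostic

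*SAP*

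**What the plan says.** SAP 9.1.2 specifies the primary MMRM for change in PSP-rating total score with "Fixed Categorical Effects: Treatment, Visit, Visit*Treatment, Sex" and "Fixed Continuous Effects: Baseline PSP-rating, Age". Protocol 11.2.3 names the same covariates: "Efficacy endpoints will be analyzed with adjustments for the baseline values as well as for the age and sex". The two documents agree.

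PSP type appears elsewhere in the plan:

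- Inclusion criterion 2 (Protocol 5.3) admits both the Richardson type (PSP-RS) and the parkinsonian type (PSP-p), with no cap or expected share of either.
- SAP 8.4.1 records type as a baseline variable.
- Protocol 11.2.6 states that "Subgroup analysis will not be considered in this clinical study". SAP 11 changes this: "Subgroup analyses for efficacy will be conducted on the endpoint related with PSP-rating scale", and on the two modified scales. Type is the only subgroup variable.
- SAP 9.2.9 to 9.2.11 add three responder endpoints restricted to the Richardson type.

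Protocol 6.3 generates the allocation "by applying a stratified block randomization method" without naming the factor. The only factor tied to allocation is site: subjects are "assigned sequentially according to the order of randomization at each study site". SAP 5.3 says that no stratification is planned. SAP 12 plans no sensitivity analysis.

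**The concern.** Type is fixed before randomisation and already collected, and the SAP treats it as worth separating in the efficacy results. The arms are small, and no text says the allocation balances type. If the two types worsen at different rates in ways that baseline score, age and sex do not capture, two things follow. A chance difference in type mix between a dose arm and placebo shifts that comparison, and between-type variation stays in the residual.

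The estimate matters because the stated purpose is to estimate an effect size for later studies (Protocol 11.4), and SAP 9.1.3 declares superiority confirmed at p below 0.05. With no sensitivity model, no type-adjusted overall estimate would be reported. Adding one after unblinding, once an imbalance had been seen, would be a post hoc choice.

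**Working it through.** **Inputs from the documents.** 20 analysed per arm, 20% dropout, 1:1:1 allocation, two-sided 5% level. The plan's only sample-size figure reproduces: 20/(1 − 0.20) = 25 per arm, 75 in total. Post-baseline PSP-rating visits are Visits 10 and 16 (Protocol 10.3.12).

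**Assumptions, because the documents give no values.** Residual SD *s* = 6 to 10 (central 8). Share of PSP-p *f* = 20% to 40% (central 30%). Difference between types in 24-week change, after baseline score, age and sex, *d* = 2 to 4 points (central 4), with 6 as an extreme.

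**1. How large an imbalance is plausible.** SD of the dose-placebo difference in type share = √(2*f*(1 − *f*)/20).

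- *f* = 0.2: 12.6 percentage points; 0.3: 14.5; 0.4: 15.5.
- By exact binomials, the chance of a difference of at least 20 points is 16% to 26% for one comparison, and 28% to 42% for at least one of the two.

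**2. What it does to the estimate.** Shift = imbalance × *d*.

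- A 20-point imbalance moves the estimate by 0.4 points (*d* = 2) or 0.8 points (*d* = 4).
- The SE is *s*√(2/20): 1.90, 2.53 and 3.16 for *s* = 6, 8 and 10.
- At central values the shift has SD 4 × 0.145 = 0.58 points, under a quarter of 2.53.

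**3. Precision.** With *s* as the residual SD before type is added, SE with type / SE without = √(1 − *d*²*f*(1 − *f*)/*s*²).

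- Smallest gain (*d* = 2, *f* = 0.2, *s* = 10): √(1 − 0.64/100), a fall of 0.3%.
- Central (*d* = 4, *f* = 0.3, *s* = 8): √(1 − 3.36/64), a fall of 2.7%.
- Largest gain (*d* = 4, *f* = 0.4, *s* = 6): √(1 − 3.84/36), a fall of 5.5%.
- For an assumed true effect of 4 points, power at the central values moves from 0.35 to 0.37.

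**4. Conditional type I error at a 2-SD imbalance.** Take *s* = 8 as the within-type SD and *f* = 0.3. The imbalance is 2 × 14.5 = 29 points. The unadjusted test estimates an SE that contains the between-type variance, so that SE sets the critical value. Given the imbalance, the estimate varies with SE 8√(2/20) = 2.53.

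| *d* | Shift | SE used by the test | Critical value (1.96 × SE) | Conditional error |
|---|---|---|---|---|
| 4 | 4 × 0.290 = 1.16 | √(64 + 3.36) × √0.1 = 2.60 | 5.09 | P(Z > 1.55) + P(Z < −2.47) = 6.7% |
| 6 | 6 × 0.290 = 1.74 | √(64 + 7.56) × √0.1 = 2.68 | 5.24 | P(Z > 1.39) + P(Z < −2.76) = 8.6% |

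**5. Over all randomisations.** A simulated week-24 ANCOVA (three arms of 20, 6000 runs per scenario, no true effect, no type term) gave mean differences of −0.05 to 0.03 and rejection rates of 0.044 to 0.054. With *d* = 4, the slope of the estimate on type imbalance was 3.7 to 4.1 without type and close to 0 with it. Where type was also related to baseline score, the unadjusted slope was 3.0 to 3.4, so the existing covariates absorbed part of the effect. With *d* = 0, adding type raised the SD of the estimate from 2.61 to 2.64.

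**6. Is a type main effect enough?** Suppose the types differ by 2 points at the first post-baseline visit and 4 at the second, with SDs 5 and 8 and correlation 0.5 (assumed). A main effect alone fits one common difference. Its GLS weights on the two visits are 44/49 and 5/49, so it estimates (44 × 2 + 5 × 4)/49 = 2.2. That leaves 4 − 2.2 = 1.8 points of the week-24 type difference unadjusted. Over equal SDs or SDs of 5 and 8, and correlations of 0.3 to 0.7, between 1.0 and 2.2 of the 4 points remain (25% to 55%). Type*visit is needed to adjust week 24 fully.

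**The case against.** The strongest reply is that covariate choice is a judgement, that protocol and SAP agree on it, and that the trial is exploratory with no statistically derived sample size. Nothing in the documents shows that type predicts progression. SAP 3.5 gives the reason for the type analyses as further exploration of efficacy, and a subgroup split looks for differing treatment effects, which is not the same as a prognostic difference. The plan also offers partial cover: SAP 8.4.2 compares type between each dose arm and placebo, so an imbalance would be seen, and SAP 11 refits the model within each type, where type imbalance cannot arise.

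Much of this stands. The omission is a design weakness, not a contradiction, and the gain may be nil. The cover is incomplete, though. Seeing an imbalance does not adjust for it, and at an assumed 30% PSP-p the parkinsonian subgroup has about 6 subjects per arm, with no planned combined estimate.

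A reader might infer that the primary estimate is biased or its type I error uncontrolled. Step 5 does not support that: the figures in step 4 hold only given an unusual imbalance. A reader might also infer that type is definitely excluded from stratification. The protocol does not name the stratification factor. Site is the only one mentioned, and this sits awkwardly with SAP 5.3, so all that can be said is that no document states type is balanced.

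**Conclusion.** The point holds as a conditional one. Type is missing from the primary model, and no sensitivity model supplies it. If type is prognostic beyond baseline score, age and sex, a chance imbalance stays unadjusted. The precision at stake is small: about 0.3% to 6% of the SE for type differences of 2 to 4 points. The conditional effect of a 2-SD imbalance is modest: 6.7% at a 4-point difference, 8.6% at a 6-point difference. All these sizes rest on assumed SD, type mix and type difference. Only the absence of the term is certain from the documents. The case for acting is that the data are already collected, the cost is slight, and the choice is credible only if made before unblinding.

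**What to change.** Before unblinding, add PSP type (PSP-RS / PSP-p) and PSP type*visit as fixed categorical effects to the MMRM in SAP 9.1.2, 9.2.1.2 and 9.2.2.2 for the full-population analyses. Sections that refer to 9.2.2.2 then follow. Drop both terms within the type subgroups of SAP 11, where they cannot be estimated. List the change in SAP 3.5, since Protocol 11.2.3 names only baseline value, age and sex.

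Cost: a few lines of text, no new data, and two degrees of freedom with two post-baseline visits. If type turns out not to be prognostic, the SE rises slightly (in the simulation, which added type as a single term, from 2.61 to 2.64).

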9.1.3 Interpret the Result

The Superiority of each study group to placebo is confirmed when the p-value for the interaction effect at 24 weeks is below 0.05.

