5. GENERAL CONSIDERATIONS FOR SUMMARIES AND ANALYSES

5.1 Significance Level

Unless otherwise specified, all statistical tests will be two-sided hypothesis tests performed at the 5% level of significance and all confidence intervals will be two-sided 95% confidence intervals.

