9. EFFICACY ANALYSES

9.1 Primary Efficacy Endpoint(s)

9.1.1 Variable, Definition and/or Derivation

Change from the baseline in the total score of PSP-rating scale after 24 weeks (6 months)

- Change from baseline at week 24 = week 24 – baseline

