3.3. Results of Past Clinical Studies

[figure not shown]
To date, GV1001 has been applied to patients with a variety of diseases through clinical studies and individual therapeutic use approval procedures. For PSP, the target disease of this clinical study, GV1001 was administered for

The PSP-rating scale (PSP-RS)¹⁴ is a measure of efficacy validated as a method of quantitatively evaluating the neurological status of patients with PSP.

**Figure 15** [Redacted content block]
[Redacted content block]

For reference, in a large-scale Phase 2/3 Davunetide clinical study¹⁶, the progression of disease in PSP patients who participated increased by 6.8 points on average after 6 months of treatment contrary to expectations, and thus, it was shown that the natural progression of worsening symptoms could not be changed.

**Figure 16** PSP-RS change in PSP patients administered Davunetide or placebo in clinical trial of NCT01110720

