10.3.12. PSP-rating scale

The PSP-rating scale evaluation will be performed at Visit 1 (screening), Visit 10, and Visit 16, and the baseline of the PSP-rating scale shall be Visit 1 (screening). At the visits requiring an evaluation of the PSP-rating scale, the subject shall make the visit in a 12-hour off-medication state for the oral drugs specified in advance. This is corresponds to a neurological examination that is directly evaluated by a neurologist who has received or is receiving a subspecialty training on dyskinesia, and the scores are summed according to a set form.^{14, 33)}

See [\[Appendix 5\]. PSP-rating scale](#) for details.

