11.2.8. Efficacy Analysis

11.2.8.1. Primary Efficacy Analysis

Descriptive statistics (number of subjects observed, mean, standard deviation, median, minimum, and maximum) will be presented by treatment group for the change from the baseline in the total score of the PSP-rating scale after 24 weeks (6 months) of investigational product administration. To test the difference between each study group and the control group (GV1001 0.56 mg/day vs. control group, GV1001 1.12 mg/day vs. control group), an MMRM analysis will be conducted with the treatment groups, visits, and interactions between the visits and the treatment groups set as fixed effects, and the subjects set as the random effect, as well as considering the baseline values, age, and sex as covariates. The results of the MMRM analysis will be summarized by LSM and standard error (SE) for each treatment group, the LSM difference between the study groups and the control group (GV1001 0.56 mg/day vs. control group, GV1001 1.12 mg/day vs. control group) and its 95% confidence interval as well as the two-side *p*-value.

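### The only decision rule for the primary endpoint (SAP 9.1.3) sets no direction and names an interaction effect where the planned analysis tests a group difference

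*SAP*

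**What the plan says.** SAP 9.1.1 defines the primary variable as the week 24 PSP-rating scale total minus baseline. SAP 9.1.2 fits an MMRM with these terms: "Fixed Categorical Effects: Treatment, Visit, Visit*Treatment, Sex", plus baseline score and age. It reports "the LSM difference between the study groups and the control group" with a 95% confidence interval and a two-sided p-value. It does not tie that difference to a visit. Protocol 11.2.8.1 gives the purpose of the same model: "To test the difference between each study group and the control group". The protocol states no success criterion.

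SAP 9.1.3 supplies one: "The Superiority of each study group to placebo is confirmed when the p-value for the interaction effect at 24 weeks is below 0.05".

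Four other places bear on how that sentence reads:

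- SAP 5.1, the default for all tests: "all statistical tests will be two-sided hypothesis tests performed at the 5% level of significance".
- Protocol 3.3, on an earlier trial in this disease, treats a rise in score as progression: it "increased by 6.8 points on average after 6 months of treatment".
- SAP 9.2.9 to 9.2.11 count subjects whose change is zero or negative, which also implies that lower is better.
- Protocol 10.3.12: "The PSP-rating scale evaluation will be performed at Visit 1 (screening), Visit 10, and Visit 16". Visit 1 is baseline, so there are two post-baseline scores. Protocol 7.1 and 10.2.9 identify Visit 16 (Week 26) as the 24-week efficacy evaluation.

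**The concern.** This sentence turns the primary result into a conclusion, so it should say what is tested, in which direction and at which visit. Two things are wrong with it.

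**Direction.** The only condition is a two-sided p-value below 0.05. A significant difference favouring placebo meets it as readily as one favouring GV1001, and the SAP nowhere states which sign is favourable.

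**Quantity.** The endpoint and the stated test concern the difference between groups in the 24-week change. The rule instead cites an interaction effect, and Visit*Treatment is itself a term in the model. A programmer who tests that term is testing a different hypothesis: whether the difference between groups changed from Visit 10 to Visit 16. Such a test can miss a benefit already established at Visit 10. Because the rule is unsigned, it can also be met by a benefit that has vanished by Visit 16.

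**Working it through.** **The plan's own figure.** 20 per group with 20% dropout: 20/(1 − 0.20) = 25, and 3 × 25 = 75, as SAP 3.3 states. The documents give no SD, correlation or target effect, so the inputs on those below are assumptions.

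**Inputs for the direction check.** n = 20 evaluable per arm (SAP 3.3). Two-sided 5% (SAP 5.1). Degrees of freedom: 60 subjects less 6 parameters (three group means, baseline, age, sex) = 54, critical value 2.005. Effects are in units of the Visit 16 SD.

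**Direction, under the likely reading (LSM contrast at Visit 16).** The standard error is √(2/20) = 0.316 SD. The noncentrality is the true worsening divided by 0.316. The chance of p<0.05 in the harmful direction is the upper tail of the noncentral t beyond 2.005:

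| True worsening | Noncentrality | Chance the rule is met |
|---|---|---|
| 0.3 SD | 0.949 | 15% |
| 0.5 SD | 1.581 | 34% |
| 0.7 SD | 2.214 | 58% |

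With the condition that the difference be below 0, these fall to 0.2% or less. Under no effect, the chance of meeting the rule falls from 5% to 2.5% per dose.

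**Quantity, only if the Visit*Treatment term itself were tested.** Let d10 and d16 be the dose-minus-placebo differences at the two visits. The LSM contrast at six months is d16; the interaction contrast is d16 − d10. Let s be the ratio of the Visit 10 SD to the Visit 16 SD and ρ their correlation. The variance of the interaction contrast is 2(1 + s² − 2ρs)/20, with s = 0.7 to 1.0 and ρ = 0.5 to 0.7 assumed. For a 0.9 SD benefit at Visit 16, where the LSM contrast has 80% power:

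- Equal benefit at both visits: d16 − d10 = 0, so the rejection rate is 5%, of which 2.5% is in the benefit direction.
- Linear growth: the SAP 6.2 window centres are days 92 and 176, so 91/175 = 52% of the benefit is present at Visit 10 and 0.9 × 0.48 = 0.432 SD remains. Power is 27% to 47%.
- Benefit only by Visit 16: d16 − d10 = 0.9 SD. Power is 80% to 97%, so nothing is lost.

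**Reverse error, on the same literal reading.** Assume a 5-point benefit at Visit 10 and none at Visit 16, SDs of 6 and 8 points, 20 per arm and a plain two-group comparison. The SD of the within-subject difference is √(36 + 64 − 96ρ), which is 8.44, 7.21 or 5.73 for ρ = 0.3, 0.5 or 0.7. Simulation (20,000 runs) gives p<0.05 in 45%, 57% or 77% of trials. The six-month contrast is significant in about 5%.

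**The case against.** The best defence is that nobody would misread the sentence. Superiority is a directional word. SAP 9.1.2 prints the LSM difference and its interval beside the p-value, so a harmful sign would be visible, and the change ≤ 0 endpoints show which way the scale runs. The references to each study group, to placebo and to a single time point all suggest the ordinary contrast at that visit, whereas a difference of differences spans two visits. SAP section 14 shows only headings in our copy and the mock tables are not included; either may identify the contrast. The trial is exploratory, its size has no statistical basis, and protocol 11.2.5 makes no adjustment for the two doses.

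Much of this stands, and it rules out several stronger readings:

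- *That the plan tests the Visit 16 minus Visit 10 difference.* The documents do not establish this. The 5%, 27–47% and 45–77% figures apply only if the likely reading is rejected.
- *That a harmful arm would be reported as superior.* The rule permits it, but the reported sign would contradict it. The 15/34/58% figures are chances of meeting the wording, not forecasts of a false claim.
- *That SAP 9.1.2 names Visit 16 and 9.1.3 departs from it.* SAP 9.1.2 names no visit. Visit 16 follows from the endpoint definition with protocol 7.1, 10.2.9 and 10.3.12.
- *That the primary time point is undefined because SAP 6.2 labels Visit 15 as Week 24.* Those protocol sections settle it: no PSP-rating assessment is planned at Visit 15. How a withdrawal score on days 157–167 enters the analysis is a separate matter for SAP 6.2 and 6.3, which rewording 9.1.3 would not resolve.

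The defence does not supply the missing sign condition, and it does not make the named quantity match the analysis.

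**Conclusion.** The point holds as a defect of wording in the sole decision rule, and should be fixed. The missing direction is a fault on any reading. Its size, 15%, 34% or 58% for a true worsening of 0.3, 0.5 or 0.7 SD, rests on 20 evaluable subjects per arm and 54 degrees of freedom. The misnamed quantity is probably loose drafting for the six-month LSM contrast; it changes the hypothesis only if taken literally, and the cost then depends on the time course of benefit, from severe when benefit is equal at both visits to none when it appears late. The consequence is confined to the stated conclusion of an exploratory trial. The estimates, standard errors and confidence intervals from SAP 9.1.2 do not change.

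**What to change.** Before unblinding, replace the sentence in SAP 9.1.3 with, for example:

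*For each dose, superiority to placebo is concluded (nominally, with no multiplicity adjustment) if the MMRM LSM difference, GV1001 minus placebo, in PSP-rating scale change from baseline at Visit 16 (the six-month efficacy evaluation) is below 0 with two-sided p<0.05.*

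Add to SAP 9.1.1 that week 24 means Visit 16 for this endpoint, and check that the section 14 code and the mock tables request the same contrast. Settle the use of withdrawal scores in the Visit 15 window separately, under SAP 6.2 and 6.3.

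The cost is one rewritten sentence and one clarification. The planned MMRM, with its Visit*Treatment term, already yields the contrast, its interval and its p-value. No new data, model change or sample size change is needed.
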